6.3.1 Unblinding

In the case of a medical emergency, such as serious adverse events (SAE), breaking the blind may become necessary during the trial

In compliance with applicable regulations, in the event of a serious unexpected adverse event (SUSAR) related to the blinded treatment, the participant's treatment code will usually be unblinded before reporting to the health authorities, ethic committees and investigators (see Section 8.3.5).

6.3.2 Emergency unblinding by the investigator

The investigator must report the blind break in conjunction with a SAE within 24 hours of becoming aware of the effect as defined in Section 10.3.1. Participants who have been unblinded will not be included in the ITT or PP efficacy analysis.

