9.3 Populations for Analyses

For purposes of analysis, the following populations are defined:

Population	Description
Safety	All participants who are randomized and take at least one dose of investigational product. Safety measures will be analyzed for all participants in the safety population.
Intent-To-Treat (ITT)	All participants in the Safety Population. ITT population will be used as the primary analysis for the efficacy parameters.
Per Protocol (PP) Population	PP population will include all participants in ITT who do not have any major protocol violations and complete the 24 hour assessments. PP population will be used as secondary to conduct the sensitivity analysis for the selected parameters.
	Major protocol deviations will be identified prior to database lock and may include but are not limited to significant violations of inclusion/exclusion criteria, noncompliance of the trial treatment taken, conditions such as vomiting and diarrhea or use of prohibited medications, and not following clinical trial protocol procedures. Any participant who rescues or vomits at or prior to 60 minutes after ingesting study medication will be excluded from the PP population.

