9.4.1 Efficacy Analyses

For each post-dose time point, Pain Intensity Differences (PID) will be derived by subtracting the pain intensity at the post-dose time point from the baseline intensity score (baseline score – post-baseline score). A positive difference is indicative of improvement. Time-weighted Sum of Pain Intensity Differences (SPIDs) will be calculated for 2, 4, 6, 8, 12, 16, 20 and 24 hours by multiplying the PID score at each post-dose time point by the duration (in hours)

Page 45 of 67

since the preceding time point and then summing these values over 0.5, 1, 1.5, 2, 3, 4, 5, 6, 7, 8, 9, 10, 11, 12, 14, (16, 18, 20 if awake), 22 and 24 hours, respectively.

Similarly, Total Pain Relief Scores (TOTPARs), will be calculated by multiplying the pain relief score at each post-dose time point by the duration (in hours) since the preceding time point and then summing these values.

In all analyses for participants who take rescue medication, all pain intensity scores after intake of rescue medication will be imputed by the worse of the baseline or the score assessed immediately before taking rescue medication. All pain relief after intake of rescue medication will be imputed by "no relief" (0).

Endpoint	Statistical Analysis Methods
Primary	The primary efficacy analyses population will be based on the ITT population.
	Sum of Pain Intensity Difference over 8 hours: SPID ₀₋₈ be analyzed using an analysis of covariance model (ANCOVA) with treatment as fixed effect and baseline pain intensity score as the covariate. A 95% of confidence interval (CI) for the treatment differences and pairwise p-values will be calculated based on the above mentioned model.
Secondary	Total Pain Relief over 8 hours: TOTPAR ₀₋₈ will be analyzed similarly as for the primary endpoint.
	Time to first use of rescue medication. If a participant did not take the rescue medication during the treatment period, (s)he will be censored at the time of last assessment. Time to first use of rescue medication will be estimated and plotted using Kaplan-Meier method and analyzed using log-rank test.

Page 46 of 67

Secondary

The SPID0-2, 0-4, 0-6, 6-12, 0-12, 12-16, 16-20, 12-24, 16-24 and 0-24 will be analyzed using the same methodology as for SPID₀₋₈.

TOTPAR0-2, 0-4, 0-6, 6-12, 0-8, 0-12, 12-16, 16-20, 12-24, 16-24 and 0-24 will be analyzed using the same methodology as for SPID₀₋₈.

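### Protocol 6.3.2 takes unblinded participants out of the ITT efficacy analysis, against the ITT definition in Protocol 9.3 and SAP 6.1, and neither document reconciles the two

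*Protocol*

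**What the plan says.** Protocol 6.3.2, on emergency unblinding by the investigator, ends with: "Participants who have been unblinded will not be included in the ITT or PP efficacy analysis". The sentence before it ties the code break to a serious event: "The investigator must report the blind break in conjunction with a SAE within 24 hours of becoming aware of the effect".

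Protocol 6.3.1 describes when codes may be broken. One case is clinical: "In the case of a medical emergency, such as serious adverse events (SAE), breaking the blind may become necessary during the trial". The other is regulatory. For a serious unexpected event related to the blinded treatment, "the participant's treatment code will usually be unblinded before reporting to the health authorities, ethic committees and investigators". Section 6.3.1 itself excludes no one from any analysis.

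Protocol 9.3 defines the Safety Population as "All participants who are randomized and take at least one dose of investigational product" and ITT as "All participants in the Safety Population. ITT population will be used as the primary analysis for the efficacy parameters". SAP 6.1 uses the same two definitions. Protocol 9.4.1 adds: "The primary efficacy analyses population will be based on the ITT population". None of these places mentions unblinding.

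The SAP does not carry the 6.3.2 exclusion. Its introduction says that it is to be read together with the protocol, and SAP 7.13 reports no changes to the analyses specified there.

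**The concern.** A dosed participant whose code is broken is in the primary analysis set under Protocol 9.3 and SAP 6.1, and out of it under Protocol 6.3.2. If such a participant occurs, the set behind SPID0-8 depends on which section the analyst follows.

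The exclusion also acts after randomisation and after dosing. Its trigger is a decision to break the code, which involves judgement and is usually prompted by a safety event that treatment may have influenced. Removing people on that basis from a set labelled ITT gives up the protection that randomisation provides. If the need to exclude someone were settled only once a case had arisen, the primary set would be chosen with knowledge of that case.

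**Working it through.** **Side by side.** Take a participant who is randomised, dosed and later unblinded.

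| Source | In Safety? | In ITT (primary)? | In PP? |
|---|---|---|---|
| Protocol 9.3 | yes | yes | depends on the PP criteria |
| SAP 6.1 | yes | yes | depends on the PP criteria |
| Protocol 6.3.2 | not addressed | no | no |

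The texts differ on ITT and no sentence in either document gives one of them precedence.

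**Timing.** SPID0-8 is complete 8 hours after dosing. Adverse events are collected until the follow-up contact (Protocol 8.3.1), 2 to 5 days after discharge (Protocol 1.3). A code broken at or after discharge cannot have affected the 0 to 8 hour scores, yet 6.3.2 removes that participant all the same.

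**Consistency with the rest of the plan.** SAP 3.1.1 has a sensitivity analysis in which dropouts for a related adverse event are kept and given their worst observation. An unblinded participant in that situation would be left out altogether under 6.3.2. SAP 7.1 reports the number in ITT but has no line for exclusions because of unblinding.

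**The plan's own scale.** Inputs from Protocol 9.2 and SAP 2.3: difference 6.5, SD 16.9, alpha 0.05, power 90%, 144 per active arm. Two-sided testing is assumed, since 95% intervals are reported.

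- n per arm = 2 × (1.960 + 1.282)² × 16.9² / 6.5² ≈ 142.1, so 143. The t-test version gives 143.03, which rounds up to the stated 144.
- Total: 3 × 144 + 2 × 48 = 528. With 5% dropout, 528 / 0.95 = 555.8, so 556.
- Standard error of the difference: 16.9 × √(2/144) = 1.99. Power at 144 per arm: 0.904.

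The plan's figures are reproduced.

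**Size of the possible shift.** If k of 144 participants are removed from one arm and their mean lies g below that arm's mean, the mean of those retained rises by k × g / (144 − k). The documents give neither k nor g, so both are assumptions.

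| k | g | Shift | Share of 6.5 |
|---|---|---|---|
| 0 | any | 0 | 0% |
| any | 0 | 0 | 0% |
| 1 | 15 | 15/143 = 0.10 | 1.6% |
| 2 | 25 | 50/142 = 0.35 | 5.4% |
| 3 | 16.9 (1 SD) | 50.7/141 = 0.36 | 5.5% |
| 3 | 25 | 75/141 = 0.53 | 8.2% |

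The largest of these is 0.53 / 1.99 = 0.27 of a standard error. Removal from the combination arm would raise the estimated difference from naproxen. Removal from the naproxen arm would lower it, and equal removals from both arms would cancel. Losing 3 from one arm takes power from 0.904 to 0.901.

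**The case against.** The strongest reply is that the SAP already settles the matter. Protocol 9 and 9.4 assign the data-handling rules and analysis populations to the SAP, and SAP 6.1 keeps everyone dosed. An analyst working from the SAP alone would retain unblinded participants. That is a fair account of what would probably happen, but it does not remove the conflict: the SAP asks to be read with the protocol and, in 7.13, declares no departure from it. Nothing tells the reader that 6.3.2 is superseded.

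The second reply is rarity. This is a single dose of over-the-counter ingredients in healthy volunteers, and Protocol 2.3 calls the medication risk low. That limits the expected size, quite possibly to zero. It is not a reason to leave the primary set ambiguous.

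Several stronger readings are tempting, and the documents do not support them:

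- *The rule drops participants with serious events.* It drops participants whose code was broken. Protocol 6.3.1 says only that a break may become necessary, so a serious event need not lead to one, and a non-serious emergency could. Those removed from efficacy are not removed from the Safety Population.
- *Every code break for regulatory reporting triggers exclusion.* The sentence is broad enough to allow this, but it stands under investigator emergency unblinding, and 6.3.1 contains no exclusion. This is one reading, not stated text.
- *Two analysts will report different primary results.* They will only if someone is unblinded.
- *The estimate is biased by several per cent.* That needs removals concentrated in one arm, all with low scores. A serious event days after dosing need not go with a poor 8-hour score.

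**Conclusion.** The contradiction is real and in current text. Protocol 6.3.2 prescribes a post-randomisation exclusion from the primary efficacy set that Protocol 9.3 and SAP 6.1 do not allow, and SAP 7.13 leaves it unresolved. The rule is wrong for an ITT analysis whatever the number affected, because membership turns on a post-dose decision that may be related to treatment, and because it discards scores recorded under blind.

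The numerical stake is small: nothing if no one is unblinded or if their scores are typical, and about 0.10 to 0.53 SPID units in one arm's mean under the assumed 1 to 3 removals with scores 15 to 25 below the mean. Power is hardly affected. The point should be corrected because the primary set must be unambiguous before lock, not because a material bias is expected.

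**What to change.** 1. In the last sentence of Protocol 6.3.2, delete the words 'ITT or', so that unblinding can at most be a reason for exclusion from PP.
2. In SAP 6.1, state before database lock that participants whose code is broken, for whatever reason, remain in ITT with their recorded scores. Note in SAP 7.13 that this departs from the current wording of Protocol 6.3.2 if the protocol has not been amended by then.
3. If wanted, add a sensitivity analysis that sets aside scores recorded after the code break. Scores from before it stay in either way.

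The protocol edit is one sentence, but an amendment needs IRB/IEC approval (Protocol 10.1.1). The SAP statement settles the analysis without waiting for that. Neither change needs new data or alters trial conduct.

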6.4 Study Intervention Compliance

The administration of the study medication will be supervised by an unblinded member of the Investigator's team. This person will perform the oral cavity inspection after study drug administration and document that the participant receives the treatment as planned.

6.5 Prior and Concomitant Therapy

The following treatments are prohibited from screening and during the study:

- Use of any form of medication or herbal supplements, including GABA and turmeric, or curcumin, within 5 days of surgery that would confound the evaluation of the study product, until discharge from the study site;
- Use of acetaminophen, naproxen, hydrocodone/acetaminophen, ibuprofen, aspirin, or other NSAIDs or any other pain reliever (OTC or prescription) within 5 days before surgery;
- Use of alcoholic beverages after midnight prior to surgery and throughout the evaluation period;

All medications (prescription and nonprescription products, vitamin and herbal products) taken by the participant from 30 days prior to Screening to End of Trial (EOT) will be documented. The reported medications will be reviewed and evaluated by the Principal Investigator or designee to determine if they affect the participant's eligibility to participate in the study.

Page 33 of 67

6.5.1 Rescue Medicine

If adequate pain relief was not achieved, then participants are permitted to take rescue medication, although they will be encouraged to wait 2 hours to allow the investigational product time to take effect. The study site will supply the rescue medication that will be obtained locally. Rescue medication will be dispensed in a hierarchical method starting with ibuprofen 400 mg. Should the participant not experience adequate pain relief, Hydrocodone 5 mg/Acetaminophen 325 mg tablets or other appropriate analgesics (such as an additional ibuprofen dose) may be used at the discretion of the Investigator. Rescue medication is also available on return of pain and the time of rescue medication will be recorded in the source documents. Pain assessments will be performed immediately before the first dose of rescue medication.

- Rating of Pain Intensity (NRS);
- Rating of Pain Relief (Categorical);
- Global Assessment of investigational product as a pain reliever.

All active stopwatch elapsed time(s) will be stopped at the time of rescue administration and recorded on the case report form.

Participants will be queried in a nonspecific fashion for any adverse events. All observed and reported AEs will be collected and recorded on the case report form. The information recorded will be based on signs and symptoms reported by the participant or observed by the research coordinator during clinical evaluation.

6.6 Dose Modification

The dosing schedule cannot be modified.

6.7 Intervention after the End of the Study

This study is a single dose administration after surgery and there is no additional treatment allocated. Participants who randomize into the study will be discharged from the study center after the final (24 hour post dosing) assessments, regardless of whether rescue medication had been taken or not.

7. Discontinuation of Study Intervention and Participant

7.1 Discontinuation of Study Intervention

See the SoA for data to be collected at the time of intervention discontinuation and follow-up and for any further evaluations that need to be completed.

Page 34 of 67

7.2 Participant Discontinuation/Withdrawal from the Study

Withdrawal criteria

Participants *must* be withdrawn from the study if any of the following occurs:

- A participant may withdraw from the study at any time at his/her own request, or may be withdrawn at any time at the discretion of the investigator for safety, behavioral, compliance, or administrative reasons. This is expected to be uncommon.
- At the time of discontinuing from the study, if possible, an early discontinuation visit should be conducted, as shown in the SoA. See SoA for data to be collected at the time of study discontinuation and follow-up and for any further evaluations that need to be completed.
- The participant will be permanently discontinued both from the study intervention and from the study at that time.
- If the participant withdraws consent for disclosure of future information, the sponsor may retain and continue to use any data collected before such a withdrawal of consent.
- Participant's pain intensity post-surgery at pre-dose does not exceed 'mild' and the NRS is <5 (see Section 10.5);
- If, in the Investigator's opinion, continuation of the study would be harmful to the participant's well-being;

Participants may be withdrawn from the study if any of the following occurs:

- Participant experiences one or more serious adverse events;
- At the specific request of the Sponsor and in consultation with the Investigator (e.g., obvious non-compliance, safety concerns);
- Protocol violation: if the participant develops conditions, which would have prevented his/her entry into the study according to the inclusion/exclusion criteria, he/she must be withdrawn immediately if safety is concerned; in other cases, the investigator will decide whether there is a conflict with the study objectives.

7.3 Lost to Follow Up

A participant will be considered lost to follow-up if he or she repeatedly fails to return for scheduled visits and is unable to be contacted by the study site.

The following actions must be taken if a participant fails to return to the clinic for a required study visit:

- The site must attempt to contact the participant and reschedule the missed visit as soon as possible and counsel the participant on the importance of maintaining the assigned visit schedule and ascertain whether or not the participant wishes to and/or should continue in the study.
- Before a participant is deemed lost to follow up, the investigator or designee must make every effort to regain contact with the participant (where possible, 3 telephone calls and, if necessary, a certified letter to the participant's last known mailing address

Page 35 of 67

or local equivalent methods). These contact attempts should be documented in the participant's medical record.

• Should the participant continue to be unreachable, he/she will be considered lost to follow up.

8. Study Assessments and Procedures

Study procedures and their timing are summarized in the SoA. Protocol waivers or exemptions are not allowed. Immediate safety concerns should be discussed with the sponsor immediately upon occurrence or awareness to determine if the participant should continue or discontinue study intervention. Adherence to the study design requirements, including those specified in the SoA, is essential and required for study conduct.

All screening evaluations must be completed and reviewed to confirm that potential participants meet all eligibility criteria. The investigator will maintain a screening log to record details of all participants screened and to confirm eligibility or record reasons for screening failure, as applicable.

Procedures conducted as part of the participant's routine clinical management (e.g., blood count) and obtained before signing of the ICF may be utilized for screening or baseline purposes provided the procedures met the protocol-specified criteria and were performed within the time frame defined in the SoA.

8.1 Efficacy Assessments

If not stated otherwise, the measures / actions listed in the following Sections 8.1.1 to 8.1.6 will be performed by a designated study team member as designated by the Principal Investigator.

8.1.1 Screening Period

Note: No screening procedures may be performed unless participants have been provided an IRB-approved written informed consent which participants have read, understood, and signed.

The Screening Period will be up to 28 days long. The following will be determined during the Screening Visit:

- Signed Informed Consent Form (ICF);
- Review inclusion and exclusion criteria;
- Participant demographics;
- Medical/surgical history including history of drug, alcohol, tobacco and caffeine use;
- Medication history of all prescription, OTC products including vitamins or dietary/herbal supplements, taken during the past 30 days;
- Vital signs consisting of sitting blood pressure (in triplicate with one min in between), respiratory rate and pulse after sitting for at least 5 minutes;

Page 36 of 67

- Physical and oral examination;
- Dental x-ray examination and interpretation including impaction score;

Note: The medical interpretation may occur after the screening visit provided a diagnosis of impaction is determined prior to surgery.

- Urine tests for illicit drugs;
- Breath or saliva alcohol test;
- Urine pregnancy test (if applicable).

Upon satisfying the inclusion/exclusion criteria, eligible participants will be instructed to return to the trial site within 28 days for oral surgery. Participants will be instructed to refrain from the use of all medications (prescription, nonprescription, herbal supplements) unless in the opinion of the Investigator or Sponsor, the medication will not interfere with study procedures, data integrity, or compromise the safety of the participants.

Participants will be instructed not to consume alcohol or use any nicotine containing products 24 hours prior to surgery. Surgery will be scheduled between 0530 h and 1030 h.

The Principal Investigator or his/her designee must review participant's study records before qualifying the participant for the trial.

8.1.2 Pre-surgery

Participants are instructed to be nil per os (NPO) from midnight prior to surgery. If a participant had something to eat or drink after midnight, the surgeon must determine if surgery may proceed. Participants will arrive at the unit at their assigned time and will have the following activities completed prior to dental surgery:

- Review changes in the participant's medical/medication history and inclusion/exclusion criteria since previous visit;
- Urine tests for illicit drugs;
- Breath or saliva alcohol test;
- Vital signs consisting of sitting blood pressure (in triplicate with one min in between), respiratory rate and pulse after sitting for at least 5 minutes (-30 minutes);
- Urine pregnancy test (if applicable);
- Review pain assessment process and procedures.

8.1.3 Impaction Score

An Impaction Score will be used to assess each tooth based on the radiographic appearance and the intraoral examination. Each tooth will be rated from 1 to 4 using the following criteria: (1) erupted in tissue (2) soft tissue impaction (3) partial bony impaction, and (4) full bony impaction. Only participants whose mandibular impactions are scored (3) or (4) will be eligible to participate in the study.

Page 37 of 67

8.1.4 **During Surgery**

During surgery, participants will be administered a short acting local anesthetic (lidocaine or mepivacaine with or without vasoconstrictor) and nitrous oxide; at the discretion of the oral surgeon. Topical anesthetics may also be used prior to the administration of the short acting local anesthetic. Long duration local anesthetics like bupivacaine are not permitted. No other perioperative analgesic or anesthetic agents are permitted. Perioperative corticosteroids are not permitted.

8.1.5 Surgical Trauma Score

At the completion of the procedure, the surgeon will rate the degree of surgical trauma on a of (1) mild, (2) moderate or (3) severe. Only individuals with a surgical trauma rating of mild (1) or moderate (2) will be eligible to participate in the study.

